7.7 CLINICAL EVENTS COMMITTEE

A Clinical Events Committee (CEC) consisting of at least 3 independent Electrophysiologists will be established to review and adjudicate all adverse events that occur during the study according to the protocol definitions. The CEC will be blinded to the investigational site and the patient identity. The CEC members will not participate as investigators, in order to minimize any potential bias.

The CEC will create a study specific charter defining the adverse event adjudication process, specifically detailing review guidelines along with appropriate response timelines.

7.8 PATIENT DEATH

Personnel at the investigational site should notify BIOTRONIK as soon as possible concerning any patient death during the investigation. This notification should include a completed Study Exit eCRF and copy of the notification of death (death report) sent to the IRB. The death report should include all of the following, if available:

- date and time of death
- place of death
- identification of the rhythm at the time of death, if known (include any available documentation)
- immediate cause of death
- any other circumstances surrounding the death
- whether the death was device related

Any implanted legally marketed devices that are explanted, including the Corox BP LV lead should be returned to BIOTRONIK for analysis.

7.9 IRB APPROVAL

Institutional Review Board (IRB) approval is required from each site prior to participation in this clinical registry. Patient enrollment may not begin until the IRB and BIOTRONIK have granted approval for the registry site. IRB approval is also required throughout the duration of this clinical investigation. If IRB approval is withdrawn for a site, BIOTRONIK must be notified within 5 working days.

7.10 OTHER INSTITUTIONS AND PHYSICIANS

This investigational registry is not transferable to other institutions attended by the investigator unless prior approval is obtained from both BIOTRONIK and the appropriate IRB. Only approved investigators are authorized to participate in the registry. However, there are certain situations where an investigator might not be immediately available to provide the necessary medical care for a patient with a registry device (e.g. when a patient goes to the emergency room for medical treatment). In any such situations, the IRB and investigator must continue to provide oversight for that patient's medical care and rights as a research subject. BIOTRONIK will ensure that the necessary support personnel are available to any physician providing immediate care for a patient in order to answer questions about the device and provide guidance in collecting the necessary documentation required for the post-approval registry. Documentation obtained will then be forwarded to the approved investigator for review and signature.

CELESTIAL REGISTRY PROTOCOL

8. RECORDS AND REPORTS

8.1 INVESTIGATOR RECORDS

The physician is required to maintain the following accurate, complete, and current records pertaining to this post-approval registry:

- All correspondence relating to the registry: e.g. with another investigator, IRB, the sponsor, a monitor, or the FDA
- Records of each patient, including case history, data forms, patient consent, and supporting documentation
- A copy of the registry protocol
- Signed investigator or research agreement
- A copy of the IRB letter approving the research registry
- A copy of the IRB approved Patient Information and Consent form
- All clinical forms and documentation, including:
 - a copy of the signed patient consent form
 - all supporting documentation for data entered into the EDC
 - records of any adverse device effects, including supporting documentation
 - records pertaining to patient deaths during the investigation
 - documentation and rationale for any deviations from the clinical protocol
 - any other records required by the sponsor

8.2 INVESTIGATOR REPORTS

The investigator is responsible for the accurate and timely preparation (review and/or signature) and submission of the reports cited below:

- Withdrawal of IRB approval and the reason for withdrawal. An investigator should report to the sponsor, within 5 working days, a withdrawal of approval by the reviewing IRB of the site investigator's participation in an investigation.
- Informed consent. If an investigator enrolls a patient without obtaining informed consent, the investigator will report such enrollment to the sponsor and the reviewing IRB within 5 working days after the event occurs.
- Notification of patient death during the post-approval registry
- Annual progress reports prepared for the IRB

CELESTIAL REGISTRY PROTOCOL

- Notification of any deviations from the investigational protocol
- Final summary report prepared for the IRB
- Other: an investigator will, upon request by a reviewing IRB, the FDA, or BIOTRONIK, provide accurate, complete, and current information about any aspect of the registry

The table below is a chart outlining the responsibilities, including time constraints, for submitting the above reports.

Type of Report	Prepared by Investigator for:	Time Constraints of Notification
Patient Death During Investigation	BIOTRONIK, IRB	BIOTRONIK as soon as possible and as required by reviewing IRB
Patient Withdrawal	BIOTRONIK	Within 5 working days
Withdrawal of IRB Approval	BIOTRONIK	Within 5 working days
Progress Report	BIOTRONIK, IRB	Submitted not less than yearly
Significant Deviations from Investigational Plan	BIOTRONIK, IRB	Within 5 working days after emergency to protect life or physical well-being of the patient, otherwise prior approval by sponsor is required
Informed Consent Not Obtained	BIOTRONIK, IRB	Within 5 working days of use
Final Summary Report	BIOTRONIK, IRB	Within 3 months after completion or termination of the registry

8.3 SPONSOR RECORDS

The sponsor, BIOTRONIK, will maintain the following records:

- All correspondence that pertains to the investigation with investigator(s), IRB, and FDA
- Investigator agreements, financial disclosures, and current curriculum vitae
- Name and address of each investigator and each IRB that is involved with the investigation
- Adverse events and complaints
- Electronic Case Report Form data
- Completed patient Informed Consent Forms
- Clinical investigational plan (protocol) and report of prior investigations
- Monitoring reports
- Clinical progress reports

8.4 SPONSOR REPORTS

The sponsor is responsible for preparing the following reports:

Type of Report	Prepared by Sponsor for:	Time Constraints of Notification
Withdrawal of IRB Approval	FDA, all reviewing IRBs, and participating investigators	Within 5 working days of receipt of notice of withdrawal of approval
Withdrawal of FDA Approval	Reviewing IRBs and participating investigators	Notification will be made within 5 working days
Progress Report	FDA, all reviewing IRBs	A periodic progress report will be submitted every six months. The report will include: 
 • All reported AEs • AE trend analysis • Patient accountability, including enrollment, and follow-up status
Recall and Disposition	FDA, all reviewing IRBs	Notification will be made within 30 working days and will include the reasons for any request that an investigator return, repair or otherwise dispose of any devices
Final Report	FDA, all reviewing IRBs, and participating investigators	Notify FDA within 30 working days of the completion or termination of the investigation. A final report will be submitted within 6 months after completion or termination of the registry.
Failure to Obtain Informed Consent	FDA	A copy of the investigator's report will be submitted within 5 working days of notification of use

APPENDIX A: DEFINITION OF TERMS

AE (Adverse Event) - an unwanted effect detected in participants. The term is used whether or not the effect can be attributed to the leads in the registry. For the purposes of this registry, BIOTRONIK classifies an AE as either related to the Corox BP lead or not related to the lead.

ACC/AHA – American College of Cardiology/American Heart Association

Cardiac Perforation – Penetration of the lead tip through the myocardium (including microperforation), either clinically suspected or confirmed by chest x-ray, fluoroscopy, echocardiogram, intracardiac electrogram and/or visually

Clinical Failure – Inability of the Corox BP LV lead to correctly sense or pace in the heart, not attributable to a mechanical malfunction of the lead or pulse generator that remains unresolved despite reprogramming and/or repositioning.

CFR – Code of Federal Regulations

Conductor Fracture – See Lead Fracture

Confirmed Failure – A Corox BP LV lead having clinically relevant characteristics that are outside the performance limits established by BIOTRONIK while implanted and in service, as confirmed by analysis, except for changes in characteristics that are due to induced malfunctions. Lead damage caused during or after explant is not considered a failure.

Complication - an adverse event that requires additional invasive intervention to resolve

Coronary Sinus Dissection – A tear that occurs in the wall of the coronary sinus

Coronary Perforation - Penetration of the lead tip through the coronary sinus, either clinically suspected or confirmed by chest x-ray, fluoroscopy, echocardiogram, intracardiac electrogram and/or visually

CHF (Congestive Heart Failure) – a condition where the heart is not able to pump sufficient amounts of blood to meet the body's need

CRT-P – Cardiac Resynchronization Therapy Pacemaker

CRT-D - Cardiac Resynchronization Therapy Defibrillator

Defibrillation Impedance – The total opposition of current that presents in the circuit utilized to shock an arrhythmic heart back into a normal rhythm. Defibrillation impedance is considered abnormal if the measurement is ≤ 20 Ohms or ≥ 200 Ohms

Diaphragmatic/Pectoral Stimulation – Clinical observation of inadvertent nerve/muscle stimulation other than cardiac muscle.

eCRF – electronic Case Report Form

EDC – Electronic Data Capture system

CELESTIAL REGISTRY PROTOCOL

Elevated Threshold – Either of the following definitions constitute an Elevated Threshold:

1. At implant, pacing thresholds for the permanently programmed electrode that are greater than 3.0 Volts at 0.5 ms., or
2. At follow-up, pacing thresholds for the permanently programmed electrode that are greater than 3.5 Volts at 0.5 ms.

ERI – Elective Replacement Indicator

Exit Block – The failure of an intact pacing system to capture the heart because the stimulation threshold exceeds the output of the pacemaker

Explanted (LV Lead) – Surgical removal of an LV lead during the acute implant stage, whereby the lead has not been chronically implanted and can be easily removed by simple traction

Extracted (LV Lead) - Surgical removal of a chronically implanted LV lead

Failure to Capture or Loss of Capture – Intermittent or complete failure to achieve cardiac stimulation at programmed output delivered outside of the cardiac refractory period

High Pacing Threshold – Sudden and significant increase compared to the previous measured threshold value

IDE – Investigational Device Exemption

Insulation Breach/Break – Visual, electrical, or radiographic evidence of a disruption or break in the insulation of a lead

IRB – Investigational Review Board

Lead Dislodgment or Lead Migration – Radiographic, electrical or electrocardiographic evidence of electrode displacement from the original implant site or electrode displacement that adversely affects pacing, and/or lead performance

Lead Fracture – Visual, electrical and/or radiographic evidence of mechanical break within the lead conductor (connectors, coils and/or electrodes)

Lead impedance out of range – Pacing impedance is considered abnormal if a measurement is ≤ 200 Ohms or ≥ 2000 Ohms

Loss of Sensing/Undersensing– Intermittent or complete failure to sense any intrinsic events that occur outside the programmed refractory periods at programmed sensitivity settings

LV – Left Ventricular

LV Lead Abandoned, CRT programmed off – The LV lead remains connected to the generator but LV pacing is disabled

Non-healing Pocket Dehiscence – Separation of wound edges around the pocket of the implanted pulse generator that have not healed

CELESTIAL REGISTRY PROTOCOL

NYHA – New York Heart Association, a recognized system of classifying patient condition according to:

- I – Ordinary physical activity does not cause undue fatigue, palpitation, dyspnea, or anginal pain
- II – Ordinary physical activity results in fatigue, palpitation, dyspnea, or anginal pain
- III – Less than ordinary physical activity causes fatigue, palpitation, dyspnea or anginal pain
- IV – Symptoms of cardiac insufficiency or of the anginal syndrome may be present even at rest. If any physical activity is undertaken, discomfort is increased

Observation – an adverse event that does not require additional invasive intervention to resolve

Oversensing – Misinterpretation of cardiac or non-cardiac events as cardiac depolarization, such as T waves, skeletal muscle potentials, and extracardiac electromagnetic interference (EMI)

PG (Pulse Generator) – For this registry, the pulse generator must be either a BIOTRONIK CRT-P or CRT-D

Pneumothorax – Air or fluid in the pleural space surrounding the lung leading to collapse or partial collapse of the lung

Premature Battery Depletion – Reaching Elective Replacement indicator (ERI) before the predicted date

Mechanical Failure – Malfunction of the Corox BP LV lead through a break in the conductor, insulation or connector pin leading to loss of CRT therapy

RV/RA/ICD lead – Right Ventricular/ Right Atrial/ Implantable Cardioverter Defibrillator Lead

Significant Increase in Pacing Threshold – One of the following definitions must be met:

1. An observed increase of 2-fold over the first chronic threshold, provided that the resultant threshold is greater than 5 Volts at 0.5 ms, or
2. An observed threshold higher than the maximum output of the device. Currently, this is 7.5 V at 1.5 ms in the Lumax 340 HF-T and Lumax 540 HF-T CRT-D's.

Chronic threshold is defined as the pacing threshold determined at the patient's 3 month follow-up visit.

Skin Erosion – Deterioration of tissue over an implanted device or the movement of a lead toward or through the skin

Suspected Generator Failure – Pulse generator issue that is potentially an electrical malfunction

CELESTIAL REGISTRY PROTOCOL

Suspected Lead Failure – Corox BP LV Lead issue that is potentially a mechanical or electrical malfunction

Tamponade – Compression of the heart caused by blood accumulation in the space between the myocardium and the pericardium

Threshold Rise – An observed threshold increase of 2-fold over the first chronic threshold, provided that the resultant threshold is greater than 3.5 Volts at 0.5 ms. Chronic threshold is defined as the pacing threshold determined at the patient's 3 month follow-up visit.

Thrombosis – The development of a blood clot in a vein or artery

Twiddler's Syndrome – A condition where the pulse generator leads are dislodged by the patient unwittingly rotating the subcutaneous pulse generator

APPENDIX B: TIMELINE

CELESTIAL Post-Approval Registry Timeline

While BIOTRONIK has legally marketed and sold cardiac rhythm management devices for many years, Cardiac Resynchronization Therapy is a relatively new field for BIOTRONIK. Creating a timeline that characterizes patient enrollment where market-share is not clearly understood is challenging, and therefore BIOTRONIK has made the following assumptions:

- FDA protocol approval by November 8, 2008
- Ability to recruit sufficient number of interested centers and enroll 2500 patients within 24 months
- 10% local IRB, 90% central IRB

In addition, BIOTRONIK assumes the approximate timeline:

CELESTIAL Post-Approval Registry Timeline Estimate	Date
FDA Approval of the Corox BP LV Leads (P070008)	May 12, 2008
BIOTRONIK Submission of CELESTIAL Post-Approval Registry	June 10, 2008
FDA Approval of CELESTIAL Post-Approval Registry	November 06, 2008
First IRB Approval	December 08, 2008
First Patient Enrolled	December 19, 2008
5 Clinical Sites open, 19 patients enrolled	February 14, 2009
CELESTIAL 6 Month Interim Post-Approval Registry Status Report submitted	May 08, 2009
50 Sites open, 223 patients enrolled	August 15, 2009
CELESTIAL 12 Month Interim Post-Approval Registry Status Report submitted	November 08, 2009
50-75 Sites open, 541 patients enrolled	February 13, 2010
CELESTIAL 18 Month Interim Post-Approval Registry Status Report submitted	May 08, 2010
50-75 Sites open, 825 patients enrolled	August 12, 2010
CELESTIAL 24 Month Interim Post-Approval Registry Status Report submitted	November 08, 2010
50-75 Sites open, 1104 patients enrolled	December 19, 2010
CELESTIAL 30 Month Interim Post-Approval Registry Status Report submitted	May 08, 2011
75-100 Sites open, 1404 patients enrolled	May 08, 2011
CELESTIAL 36 Month Interim Post-Approval Registry Status Report submitted	November 08, 2011
75-100 Sites open, 1854 patients enrolled	November 08, 2011
75-100 Sites open, 2000 patients enrolled	February 08, 2012
CELESTIAL 42 Month Interim Post-Approval Registry Status Report submitted	May 08, 2012
75-100 Sites open, 2225 patients enrolled	May 08, 2012
75-100 Sites open, 2500 patients enrolled	August 29, 2012
CELESTIAL 48 Month Interim Post-Approval Registry Status Report submitted	November 08, 2012
CELESTIAL 54 Month Interim Post-Approval Registry Status Report submitted	May 08, 2013
CELESTIAL 60 Month Interim Post-Approval Registry Status Report submitted	November 08, 2013
CELESTIAL 66 Month Interim Post-Approval Registry Status Report submitted	May 08, 2014
CELESTIAL 72 Month Interim Post-Approval Registry Status Report submitted	November 08, 2014
CELESTIAL 78 Month Interim Post-Approval Registry Status Report submitted	May 08, 2015
CELESTIAL 84 Month Interim Post-Approval Registry Status Report submitted	November 08, 2015
CELESTIAL 90 Month Interim Post-Approval Registry Status Report submitted	May 08, 2016
CELESTIAL 96 Month Interim Post-Approval Registry Status Report submitted	November 08, 2016
CELESTIAL 102 Month Interim Post-Approval Registry Status Report submitted	May 08, 2017
CELESTIAL Final Post-Approval Registry Status Report submitted	November 08, 2017

# 1. INTRODUCTION

The CELESTIAL study is a post-approval registry of the BIOTRONIK Corox OTW BP, Corox OTW-S BP, and Corox OTW-L BP Left Ventricular (LV) pacing leads, also referred to as "Corox LV". For this study, the Corox lead is utilized in conjunction with any US market-released BIOTRONIK CRT-D or CRT-P devices. The study is conducted to confirm the long-term safety and effectiveness of the Corox LV leads as used in conjunction with a BIOTRONIK Cardiac Resynchronization Therapy (CRT) device. The study also provides data to permit characterization of any Corox LV lead failures contributing to subjects losing CRT therapy. The Corox LV leads are capable of providing permanent pacing therapy to the left ventricle in a CRT system. Subjects enrolled in this study will be followed for five years post-implant.

## 1.1 SAMPLE SIZE AND POWER

The estimated sample size requirement is based on both primary safety endpoints: a noninferiority comparison of the overall serious adverse event (SAE) free-rate to 92.5% at 5 years, excluding those SAEs listed in Protocol Table 4, and a non-powered, superiority comparison for those individual lead-related SAE to 1% at 5 years. The sample size for primary safety endpoint 1 was calculated based on the following assumptions:

### Assumptions for primary safety endpoint 1

- Study Design: nonrandomized registry
- Type I error (alpha): 0.05 (one-sided for noninferiority)
- Statistical power: 80%
- Noninferiority delta: 5%
- Estimated SAE-Free Rate at 5 years: 92.5% for Corox BP LV Leads

For primary safety endpoint 1, a total of 240 evaluable subjects implanted with Corox BP LV leads would be required to demonstrate the noninferiority within 5% of a SAE free-rate of 92.5%. Assuming a 50% loss to follow-up rate over 5 years of follow-up, a total of 480 (240/0.5) subjects would be required to evaluate primary safety endpoint 1. Enrollment will seek to achieve 240 evaluable subjects for each of the Corox BP LV leads.

### Assumptions for primary safety endpoint 2

- Estimated individual SAE rate at 5 years: 0.4%
- Allowable two-sided, upper 95% confidence bound: 1%

For primary safety endpoint 2, a total of 1000 subjects would be required to demonstrate a two-sided, upper 95% confidence bound of 1%, assuming an expected individual SAE rate of 0.4% (no more than 4 patients with an SAE out of 1000). Assuming a 50% loss to follow-up rate over 5 years (10% per year), a total of 2000 (1000/0.5) enrolled patients would be required for evaluation of primary safety endpoint 2.

## 2. STUDY ENDPOINTS

### 2.1 PRIMARY ENDPOINT 1: SAFETY OF COROX BP LV LEADS PACING – OVERALL COMPLICATION-FREE RATE

The primary safety endpoint will be evaluated in the following testable hypothesis in a noninferiority format.

$H_0$ : The serious adverse event-free rate (SAEFR) for the Corox LV Leads at 5 years post-enrollment is inferior to 92.5%

$$\text{SAEFR} + \delta \leq 92.5\%$$

$H_a$ : The serious adverse event-free rate (SAEFR) for the Corox LV Leads at 5 year post-enrollment is not inferior to 92.5%

$$\text{SAEFR} + \delta > 92.5\%$$

Where, ( $\delta$ ) is the clinically significant difference for establishing noninferiority. A rejection of the null hypothesis would indicate that the serious adverse event-free rate is not inferior to 92.5% within ( $\delta$ ).

### 2.2 PRIMARY ENDPOINT 2: SAFETY OF COROX BP LV LEADS PACING – INDIVIDUAL COMPLICATION RATES

Each of the individual types of serious adverse events contributing to primary safety endpoint 1 will be evaluated separately in the following superiority hypotheses:

$H_0$ : The individual serious adverse event rate (SAEIndividual) for a given type of SAE for the Corox LV Leads at 5 years post-enrollment is equal to 1%

$$\text{SAEIndividual} = 1\%$$

$H_a$ : The individual serious adverse event rate (SAEIndividual) for a given type of SAE for the Corox LV Leads at 5 years post-enrollment is not equal to 1%

$$\text{SAEIndividual} \neq 1\%$$

If the two-sided, 95% upper confidence bound is no more than 1% for individual serious adverse events, then the null hypothesis will be rejected for that SAE type.

### 2.3 SECONDARY ENDPOINTS

There were no pre-specified formal hypotheses established for the following secondary endpoints:

1. Successful biventricular pacing in a BIOTRONIK CRT device at scheduled CELESTIAL registry follow-up visits through 5 years post-enrollment
2. Serious adverse event rates for SAEs excluded from primary safety endpoint (listed in Protocol Table 4) through 5 years post-enrollment.
3. Pacing threshold, sensing and impedance measurements for the Corox BP leads at scheduled CELESTIAL registry through 5 years post-enrollment
4. Individual electrical parameters of the Corox OTW BP LV lead, the Corox OTW-S BP LV lead, and the Corox OTW-L BP LV lead.
5. Overall incidence of serious adverse events that meet the primary endpoint 1 criteria will be evaluated separately for each Corox BP lead model.

6. Incidence of individual types of serious adverse events contributing to primary endpoint 2 will be evaluated separately for each Corox BP lead model.

## 2.4 FDA REQUESTED AD HOC ANALYSIS

The FDA had requested an ad hoc analysis in P070008/R4, which includes: chronic events that occur at 30 or more days post-implant; lead dislodgements occurring 30 or more days post-implant; elevated LV pacing threshold, intermittent LV capture, and no capture of LV lead occurring 30 or more days post-implant; diaphragmatic stimulation occurring 30 or more days post-implant; and all LV lead related perforations. This analysis differs from the protocol specified primary endpoint analysis by including adverse events which, per protocol, are excluded from the primary analysis if they occur 30 or more days post-implant, changing the time frame for lead dislodgements from 180 or more days post-implant to 30 or more days post-implant, including all LV lead related perforations, and excluding other events that occur within less than 30 days of implant. In addition, all subjects with an elevated pacing threshold obtained at a routine follow-up visit that occurred 30 days or more post-implant are included regardless of whether the event met the criteria for a protocol defined adverse event.

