3.2.4 Enrollment Visit (within 30 days of screening visit)

After Informed Consent has been obtained and the patient has been determined to be eligible for the registry, data is collected in the Enrollment Visit. Typically the Screening Visit and the Enrollment Visit happen concurrently.

The following are required at the Enrollment Visit:

- Collect retrospective implant information from medical chart review
 - Date of implant
 - Implant approach/method, and venous access
 - Implant location of pulse generator and implanted leads
 - Implant procedure durations, if available
- Collect patient demographics (gender, height, weight, etc.)
- Medical history of patient
 - Bradycardia or ICD indication with Heart Failure
 - NYHA classification
 - LVEF %, if available; date and method obtained
- Collect information on implanted system (pulse generator and leads manufacturer/model, serial numbers, etc.)
- Record electrical parameters of the implanted leads
- Record any cardiac related adverse event between implant and the enrollment visit

Programming parameters should be set to best suit the needs of the patient. If adequate system function, including effective CRT, cannot be obtained, the patient should not be enrolled in this registry.

CELESTIAL REGISTRY PROTOCOL

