3.2.5 Routine and Unscheduled Follow-Ups

Patients enrolled in the CELESTIAL post approval registry can be implanted with either a CRT Pacemaker (CRT-P) or a CRT Defibrillator (CRT-D). Follow-up schedules for these devices vary by practice, but typically occur every 3-4 months for a CRT-D and every 6 months for a CRT-P. Therefore patients will be seen for routine follow-up visits per their institutional standard of care, but not to exceed every 6 months. All scheduled follow up windows are ± 1 month.

Any time a patient is seen outside of a required follow-up window according to each site's pre-determined specific follow-up scheduling practice, that visit is considered an unscheduled follow-up. Each site Principal Investigator (PI) and Clinical Research Coordinator (CRC) will be trained to identify and schedule follow-ups to meet this expectation. Additionally, the EDC will provide assistance in identifying properly scheduled follow-ups according to this protocol by assisting in the selection of the proper electronic Case Report Form (eCRF).

The following are required at each follow-up visit:

- Interrogate programmed parameters
- Determine lead electrical parameters
- Evaluate device diagnostics and programmed parameters to ensure CRT is programmed "ON" and the device is correctly providing CRT therapy
- Record % of CRT pacing
- Determine if there are any cardiac-related Adverse Events. If there are, complete the Adverse Event eCRF
- Complete all appropriate eCRF's

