- Lead impedance out of range, high impedance
- Lead impedance out of range, low impedance
- Lead related thrombosis
- Implant damage to lead (e.g. accidental cut to lead body during pocket revision, device replacement, etc.)
- Premature battery depletion
- Suspected lead failure
- Suspected generator failure
- Twiddler's Syndrome
- Lead undersensing or loss of sensing
- Skin erosion

Condition Two:

- Lead pacing polarity or pacing mode reprogrammed due to suspected lead failure
- Lead surgically repositioned
- Lead surgically explanted
- Lead surgically replaced
- Lead surgically abandoned
- Lead abandoned and pacing disabled
- Lead use continued based on medical judgment despite a known clinical performance issue
- Other lead related surgery performed

Note: If Condition One is corrected by reprogramming the pulse generator or lead (other than changing the polarity or pacing mode) and no other invasive action was taken, then the event will not be considered an adverse event and should not be reported. Similarly, programming changes in pacing polarity/vector or pacing mode that are not due to a suspected lead failure will likewise not be considered an adverse event and should not be reported. For example, electrical reprogramming of the pacing polarity to eliminate diaphragmatic stimulation will not be considered an adverse event.

The adverse events that the IRB considers reportable are dependent on the particular IRB. The protocol-defined Adverse Events not related to the Corox BP LV lead are detailed in Table 4. To avoid underreporting, BIOTRONIK recommends that, at a minimum, the investigational site reports the adverse events detailed above that occur during the CELESTIAL post approval study to BIOTRONIK and their IRB.

The investigational site should report the Adverse Event on the Adverse Event eCRF. Additionally, registry sites may report adverse events through MedWatch, FDA's adverse event reporting tool for market-released devices. As defined in BIOTRONIK's internal procedures, these adverse events may be reported by BIOTRONIK through manufacturer's MedWatch reports.

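### The FDA-requested analysis counts elevated thresholds that are not adverse events only when read at a routine follow-up visit, so some elevated readings at enrollment or unscheduled visits are dropped or dated late

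*SAP*

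**What the plan says.** SAP 2.4 gives two ways into the FDA-requested analysis.

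- **Event route.** It covers "elevated LV pacing threshold, intermittent LV capture, and no capture of LV lead occurring 30 or more days post-implant". The next sentence describes the change from the primary analysis as "including adverse events which, per protocol, are excluded from the primary analysis if they occur 30 or more days post-implant". No visit type is required.
- **Reading route.** As an addition, "all subjects with an elevated pacing threshold obtained at a routine follow-up visit that occurred 30 days or more post-implant are included", whether or not the finding was a protocol adverse event.

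SAP 5.4 reports the result in the ITT population as event rates, a Kaplan-Meier graph and the estimated 5-year freedom from event with standard error and 95% confidence interval.

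The Protocol separates the visit types. Section 3.2.2 lists enrollment apart from routine and unscheduled follow-ups. When a subject attends at a time that does not fit the window set by the site's own schedule, section 3.2.5 rules: "that visit is considered an unscheduled follow-up". Windows are ±1 month. Measurements are required at enrollment (Protocol 3.2.4: "Record electrical parameters of the implanted leads") and, under 3.2.5, at every follow-up, routine or unscheduled.

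Appendix A defines an elevated threshold after implant as: "At follow-up, pacing thresholds for the permanently programmed electrode that are greater than 3.5 Volts at 0.5 ms".

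**The concern.** The reading route exists because adverse event reporting does not capture every elevated threshold. Limiting it to routine follow-up visits leaves out other occasions on which the same quantity is measured and recorded, including early visits prompted by symptoms and routine checks that slip outside their window. The SAP gives no reason for the limit.

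At stake is a descriptive result: the 5-year freedom from event prepared at the FDA's request. If collected elevated readings are dropped or dated late, that figure makes the lead look better than the recorded data do.

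**Working it through.** The plan states no figure for this point, so the check is mainly a reading of the definitions side by side.

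**Step 1: does the event route recover readings that the reading route leaves out?** Protocol 7.6 requires a Condition One finding and a Condition Two action together.

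- Condition Two includes surgical repositioning, explant, replacement or abandonment, disabling pacing, a polarity or mode change for suspected lead failure, and continued use on medical judgment despite a known performance issue. With a Condition One finding, any of these makes an adverse event at any visit, and the event route picks it up.
- A problem corrected by other reprogramming is not reportable. In addition, "programming changes in pacing polarity/vector or pacing mode that are not due to a suspected lead failure will likewise not be considered an adverse event". These cases do not enter by the event route.
- Condition One refers to a high pacing threshold, which Appendix A defines as a sudden and significant rise over the previous value. An elevated threshold is an absolute level, above 3.5 V at 0.5 ms. A reading can be elevated without meeting Condition One.

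**Step 2: trace an elevated reading at 30 or more days, taken at enrollment or an unscheduled visit.**

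- It meets both conditions: counted as an adverse event.
- It is no adverse event and persists to the next routine visit: counted, but dated there. Raising the output belongs here, because it does not lower the measured threshold.
- It is no adverse event and resolves by itself first: not counted.
- It is no adverse event and is removed by a vector or mode change not attributed to lead failure: not counted. The definition follows the permanently programmed electrode, so the next reading may be on a different configuration.
- It is no adverse event and the subject dies, exits or has no later routine reading: not counted. The plan assumes 50% attrition over 5 years (Protocol 2.6).

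**Step 3: how much of the schedule lies outside the reading route?**

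- Enrollment is allowed on days 7 to 180. Days in the window: 180 − 7 + 1 = 174. Days at 30 or later: 180 − 30 + 1 = 151. Share: 151/174 = 86.8%.
- Calendar time outside a ±1 month window is 1 − 2/(interval in months): 1 − 2/3 = 33% (3-monthly), 1 − 2/4 = 50% (4-monthly), 1 − 2/6 = 67% (6-monthly).

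These are shares of calendar time, not of visits or elevated readings.

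**Step 4: direction.** Let T be the event time if every recorded reading counts, and T′ the time under SAP 2.4, infinite if the reading never counts. T′ ≥ T for every subject, so P(T′ > 5 years) ≥ P(T > 5 years). Under independent censoring, Kaplan-Meier estimates the first where the second is wanted, so the bias is upward or zero. This is a statement about expectation. In one data set, an event moved to a later, smaller risk set takes a slightly larger step, so re-dating alone need not raise the realised 5-year value.

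**Step 5: scale per subject.** One omitted subject moves the estimate by at most about 1/n at risk: 1/2500 = 0.04 percentage points with the whole planned cohort at risk, and 1/(2500 × 0.5) = 0.08 points at the planned attrition. This is a conversion factor only. The documents do not give the number of such subjects.

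**The case against.** A reader might infer that SAP 2.4 disregards every threshold problem found outside a routine visit, or that any problem corrected before the next routine visit is missed. The documents support neither reading. The routine-visit sentence adds to an event list that has no visit restriction, and Condition Two recovers many corrected or tolerated cases.

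Other points on the plan's side:

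- **Broad reading of the event list.** If it already covered every elevated threshold, adverse event or not, there would be no gap. The added sentence would then be redundant, so the narrower reading fits better. If the broad one was meant, the text should say so.
- **The FDA request is not among the documents.** The routine-visit wording may have been agreed there. This stands, and it shapes the fix.
- **Even ascertainment.** Readings on a fixed schedule are less driven by symptoms, and secondary endpoints 3 and 4 also use scheduled visits. That suits a summary of average thresholds. It is weaker for an analysis asking whether a subject ever had an elevated reading, and the SAP does not state it as the reason.
- **Enrollment readings.** Protocol 3.2.4 bars enrollment when adequate system function, including effective CRT, cannot be obtained, which removes some cases. Appendix A has separate implant (above 3.0 V) and follow-up (above 3.5 V) limits and does not say which applies at enrollment. Both points stand; the second must be settled in the text.
- **Descriptive status.** The analysis has no hypothesis, margin or decision rule. This stands and limits the severity.

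**Conclusion.** The concern holds in a limited form and is minor. Followed as written, SAP 2.4 drops elevated readings from enrollment and unscheduled visits that never become adverse events and are not elevated at a later routine visit, and it dates persistent ones late. Relative to counting all recorded readings, bias in the 5-year freedom from event can only be upward, assuming independent censoring. The primary endpoints, their error rate and the sample size are unaffected.

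The size cannot be computed: the documents give neither visit counts nor a rate of non-adverse-event elevations. A reader might take the 3.6 to 5.6% in Protocol Table 4, which is 2500 × 0.036 = 90 to 2500 × 0.056 = 140 patients, and assume that a share of these is lost. The documents do not support that. The row gives prior-study rates of serious adverse events and combines high threshold with intermittent and absent capture. Adverse events of that kind enter by the event route whatever the visit, so the row does not measure the readings at issue.

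**What to change.** In SAP 2.4, extend the reading route to any visit with a recorded threshold (enrollment, routine or unscheduled) at 30 or more days post-implant. State that the Appendix A follow-up definition applies to all these readings, including those at enrollment, and that the event is dated at the first such reading. SAP 5.4 should also state how subjects already elevated at enrollment enter the Kaplan-Meier analysis.

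If the FDA request specified routine visits, keep that version and report the any-visit version beside it.

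The cost is a short SAP edit and minor extra programming. The protocol already requires the measurements, so no new data collection is needed. The descriptive rate may become slightly less favourable.
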